## 3. Study Design

**Describe all study procedures, materials, and methods of data collection:**

[figure not shown]
Our project includes several components, as depicted in the following research project diagrams:

**Figure 1.**

Revised 7/19/2018 (New components in red)

## 1. Focus groups (Online & Local) & Survey (Phase 1)

Online Focus Groups- The research team will develop HPV vaccine themes/messages/campaign materials intended for parents of children 9-14 years old, based on literature review of common parent attitudes toward the HPV vaccine (e.g., it's not necessary, it's not safe, it's only for sexually-active people)—See enclosed recruitment messaging that addressing the themes/messages we'd like to consider for message-testing in Phase 2 (pictures with the messages will vary based on bank of images available through Facebook at time of recruitment). In Phase 1A, the research team will facilitate discussions on the themes via Facebook ads and comment features to identify messages for testing in Phase 2 and develop candidate message/campaign materials in Phase 3. The questions asked in the Facebook ads for discussion have been formed by integrative health behavior model by Fishbein and Yzer (See enclosed recruitment messaging for questions). Using Facebook ads and anonymous survey feedback data for campaign themes, we will collect up to 2,000 comments about the themes/questions. Messages that elicit strong emotional disturbance, negative affect, and negative feedback will be removed from the comments list. A similar set of discussion questions will be used to facilitate traditional, in-person focus groups in New Hampshire and Vermont (described below), for determining reliability of the Facebook discussion method and to help shape the messages for testing in Phase 2.

Survey (Online)- In addition to the public form of focus group discussions available via comments under Facebook ads, we will also have an external survey (Phase 1B, through Qualtrics—See enclosed survey questions) embedded on the Facebook ads to allow participants to privately share their written feedback. For those who are interested in participating in further survey questions may continue after they provide comments responding to the questions posed in the Facebook ads. Previously approved methods using MTurk for this phase has been removed from the study design. *Sample size and recruitment:*

- i. Facebook: We will recruit using stratified sampling by geo-targeting the Facebook ads to recruit from predominantly-rural ZIP codes and predominantly-urban ZIP codes (as defined by Rural-Urban Commuting Area (RUCA) Codes) from New Hampshire and Vermont. We will also work with Facebook's ad features to have the ad primarily presented to parents with 9-14 year old children. With six different themes/sets of questions to test, we will have up to 12 ads/strata (one urban and one rural for each of the six themes). There is an eligibility screener at the beginning of the survey.
- b) *Data collection methods:* See enclosed recruitment messages to review the focus group questions that people will provide public comments on. See enclosed survey to review all possible questions we may ask; we expect to reduce the number of questions, but have provided all possible questions for CPHS review. The survey will be administered via Qualtrics for those recruited from Facebook. Any contact information will be collected via a link to a separate Qualtrics survey to ensure contact information is maintained separate from survey responses. Participants will be debriefed with factual information about the HPV vaccine (e.g., from the Centers for Disease Control and Prevention or American Cancer Society).
- c) *Participant compensation:* Survey participants recruited through Facebook (Phase 1B) will have the opportunity to enter a prize drawing for up to 80, \$5 gift cards/online gift codes. As of 7/19/2018, only four people have provided their contact information for prize drawing entry; we will award all four of them a \$5 gift card and will then reduce the number eligible to win to 80 (rather than 120). This will be updated in our information sheet for any new study participants.
- d) *Eligibility:* For Facebook recruitment, we will geo-target the Facebook ads to recruit from predominantly-rural ZIP codes and predominantly-urban ZIP codes (as defined by Rural-Urban Commuting Area (RUCA) Codes). Anyone viewing the ad will be eligible to leave comments. Those people interested in answering the private survey (whether recruited through Facebook) will need to confirm their ZIP code, state of residence, and that they have a child 9-14 years old for inclusion, as eligibility will be limited to parents with children 9-14 years old living in New Hampshire or Vermont. In addition to our actual screening questions to ensure the prospective participant meets our eligibility criteria, we will ask some dummy questions, to avoid deception.

As needed, we may post additional advertisements to Facebook just to recruit for survey completion (without inviting people to leave public comments).

e) *Confidentiality and Protections:* For the online focus group comments, Facebook users viewing the ad will receive a disclaimer that any comments will be publicly-available and viewable by others (See enclosed recruitment messaging). For the private surveys, data will be collected online through Qualtrics and on paper for people participating in the local focus groups (described below). Any electronic survey data will be stored on password-protected computers and will only be viewable to CITI-trained research team members through Qualtrics portal and/or through this project's Dartmouth-hosted SharePoint site that is only accessible to the research team members via password. After data are no longer needed, they will be destroyed by the research team, and destruction will be confirmed by the information technology team at the Norris Cotton Cancer Center/Geisel School of Medicine. Further, participants who provide their contact information will do so via a separate survey link to ensure their contact information is collected and maintained separate from their survey data. We will ask demographic information, but these self-reported responses will be anonymized and paired with a random Study ID number. Responses will never be linked to any identifying information.

Local Focus Groups with Surveys- In addition to online focus groups and surveys, we will conduct traditional in-person focus groups with parents of children 9-14 years old living in New Hampshire and Vermont. This will enable us to validate the information received during the online focus groups and compare methodologies.

- a) *Sample size and recruitment:* We will recruit through advertisements in New Hampshire and Vermont communities (see recruitment messaging), including but not limited to newspaper advertisements, social media advertisements, flyers in primary care/medical practices, announcements in community listservs, in-person recruitment at community venues, and bulletin board postings.
- b) *Data collection methods:* Prospective participants may complete a telephone screening call and, if eligible, will receive a brief description of the study verbally from a CITI-trained research team member, and the participant will have the opportunity to ask questions. The eligibility screening will consist of the following questions:
  - a. Are you a parent?
  - b. Do you have at least one child between the ages of 9 and 14 years old?
  - c. Are you a resident of New Hampshire or Vermont?

At the time of the focus group, a consent form will be reviewed, participants will again have the opportunity to ask questions, and signatures will be obtained. See enclosed consent form.

Focus groups are expected to take approximately 75 minutes (60-90 minutes) and will take place at local sites throughout New Hampshire and Vermont (e.g., at the YMCA, schools, libraries, community centers). We will recruit through advertisements in the communities (see recruitment messaging), including but not limited to newspaper advertisements, social media advertisements, flyers in primary care/medical practices, in-person recruitment at community venues, and bulletin board postings.

Notes will be taken during the focus groups, and the sessions will be audio recorded; we may consider using a free or paid service for audio transcriptions.

We will also ask participants to complete an anonymous survey to provide more of their attitudes and beliefs about the HPV vaccine in a more private way, as we have done with the online focus groups. We will use the same survey/questionnaire that we are using for the online focus groups' survey (previously approved by CPHS), with minor edits (see enclosed with tracked changes); depending on timing, we may reduce the number of questions presented in the survey.

At the end of the focus groups, we will also ask participants if they have interest in providing future input to the cancer center as part of the cancer center's Community Advisory Board and/or if they have an interest in being contacted about future research opportunities—including a follow-up survey about this project (Cohort 1). Information about the Community Advisory Board will be provided, and contact information will be obtained from anyone interested in learning more about the Community Advisory Board and/or research opportunities.

- c) *Participant Compensation:* Participants will be compensated \$20-\$40 depending on the level of participation/time involved. Meals or snacks may also be provided.
- d) *Eligibility:* Eligibility will be based on verbal screening of the following three questions:
  - a. Are you a parent?
  - b. Do you have at least one child between the ages of 9 and 14 years old?
  - c. Are you a resident of New Hampshire or Vermont?
- e) *Confidentiality & Protections:*
  - a. *Administrative:* Efforts will be made to protect the identities of the participants and the confidentiality of the research data used in this study. Any data that are made publicly available will be presented in aggregate so that no one participant can be identified through the data. Additionally, participants will have the opportunity to use a pseudonym during the focus groups, and the transcript will not include any names; rather, we will refer to the participants more generally such as "Mother 1" and "Father 1."
  - b. *Physical:* All paper records, such as signed consent forms, will be stored in a locked cabinet in a locked office at DHMC.
  - c. *Technical:* Access to all electronic files will be limited to CITI-trained research team members. Audio recordings of the focus groups will be destroyed after transcription. Electronic data will be stored on secure servers housed at DHMC with appropriate backup and will be shared across the research team using the research team's password-protected SharePoint site hosted by Dartmouth.

2. **Online message testing (Phase 2)** - Once the list of strong candidate themes is finalized, we will test the effects of those theme-relevant messages/materials on changing knowledge, attitudes, beliefs, and behavioral intentions of parents of children 9-14 years old living in New Hampshire and Vermont; (parents of any age child are invited to complete the survey as well, excluding questions related to vaccination history and intention to vaccinate). The message testing phase will involve pre/post-test designs. Prior to the message-testing phase (Phase 2), if needed, we will conduct anonymous online pilot surveys through Qualtrics. Prior to the message testing, this pilot test is to check the validity of each message (e.g., ensuring that the stimulus materials -campaign messages- are presented and perceived by audiences as we intended for positive effects).

To test the persuasion effects of candidate messages, we will measure an array of constructs in the pre-test stage (before exposure to materials/messages). A list of the candidate constructs that are critical in understanding message effectiveness include: prior knowledge, pre-existing attitudes, normative beliefs, response efficacy, and issue involvement. After finishing pre-test assessments, participants will be randomly assigned to one of the conditions and asked to read/review the stimulus material/message while experimentally controlling for high elaboration likelihood. After the message exposure step, participants will be asked to answer post-test survey measures, including: persuasiveness of the viewed message/material, attitude toward behavior promoted, response efficacy, behavioral intention, and normative belief assessment. A full list of finalized survey questionnaires and messages will be submitted in a future modification to this study, before the online message testing commences.

- a) *Sample size and recruitment:* We expect to test a finalized set of messages, up to approximately 40 messages, with up to 30 people evaluating each message; as such, we will recruit maximum 1,200 people to complete message testing via various media recruitment and platforms (including Amazon Mechanical Turk and social media advertisements). For message testing

[figure not shown]
experiments, we implement two different cohort studies (Cohort 2A and 2B in Figure 1). Additional people will be screened for eligibility.

**Cohort Phase 1B:** Previously IRB-approved Cohort 1B is no longer part of this study design. We did not have large enough sample size to conduct a time-lag follow-up study, thus this Cohort 1B is removed from the project.

**Cohort Phase 2A:** We use paid advertisements on social media and MTurk to recruit residents in VT and NH. An external link to Qualtrics surveys will be embedded in the ads and in the MTurk posting. The message testing study will be held on Qualtrics. We will measure same constructs and examine an identical set of candidate messages across two cohorts. This cohort will not have a time-lag between pre- and post-assessments.

**Cohort Phase 2B:** We will implement the same message testing study and recruit participants in the US via Mturk and social media advertisements (e.g., Facebook ads). MTurk is an online labor market with more than 500,000 active members where requesters distribute small tasks, and workers complete the tasks for compensation as low as 1 cent in US dollars. More than 345,000 tasks are available on MTurk to anonymous workers to complete. The cohort will be invited to the same message-testing experiments with identical pre- and post-assessments used in Cohort 1B and Cohort 2A. The data from this national pool of participants will be used as reference points. This cohort does not have a time-lag between pre- and post-assessments.

**b) Data collection methods:** After recruitment, we will screen participants for eligibility (criteria described below) with a Qualtrics-administered survey that asks the participant a series of questions that include the eligibility criteria as well as some dummy questions, to avoid deception on part of the prospective participant (see enclosed pre/post test survey). They will be asked to read the information sheet to proceed. Once they click the NEXT button to provide implicit consent to participate in the study, they will be asked to click on a link to the survey hosted on Qualtrics. They will be asked to answer pre-test questions. Cohort 1B will end survey and will be followed-up later for a random assignment for message exposure and post-assessments (for those who provide email address or MTurk worker ID number). After finishing pre-test, (without any time-lag), participants in Cohort 2A and 2B will be randomly assigned to one of the advertisement/message conditions in the following page. For message exposure, participants will be asked to carefully view the assigned message/material, and then answer a series of post-test questions. When participants finish the entire questionnaires, they will be debriefed and provided with useful resources about HPV. MTurk participants (Cohort 2B) will be asked to enter their worker ID (to verify their participation for compensation on Amazon Mechanical Turk). Eligible participants recruited from social media (Cohort 2A and 2B) who want to receive study compensation will have a chance to enter their contact email address for one of e-gift cards (to be sent to randomly selected participants). Eligible participants recruited from MTurk (Cohort 2A, and 2B) will be asked to provide their MTurk Worker ID number before being paid (amount described below). See enclosed document with examples of messages that participants could be exposed to/randomized to.

**c) Participant compensation:** Participants recruited from social media platforms (Cohort 2A and 2B) will have a chance to receive one of 50 e-gift cards worth up to \$10. Participants recruited through MTurk will be compensated as MTurk workers using their worker ID numbers. We estimate the screening questionnaire to take approximately up to 5 minutes and will compensate

people up to \$0.50 for completing the screener. We estimate the actual survey/message testing to take about 15 minutes per participant. For those recruited through MTurk, based on typical MTurk payment amounts and based on [name] extensive experience with MTurk, we estimate each MTurk worker to receive up to \$1.50 for 15 minutes of message testing. This payment amount is in-line with typical payment amounts expected on MTurk (\$0.10/minute).

- d) *Eligibility:* Participants must be parents with at least one child who is 9-14 year old child living in New Hampshire or Vermont to complete the entire survey as part of Cohort 2A and in the US for Cohort 2B (parents with any age children are invited to complete the survey, excluding questions related to vaccination history and intention to vaccinate their 9-14 year old child/ren). The survey will contain a set of screening questions (as described earlier) to determine eligibility; geographic eligibility will be determined based on self-reported zip code/state and geo-targeting tools available on social media platforms.
- e) *Confidentiality and Protections:* Data will be collected online through Qualtrics. Any electronic data will be stored on password-protected computers and will only be viewable to CITI-trained research team members through Qualtrics portal and/or through this project's Dartmouth-hosted SharePoint site that is only accessible to the research team members via password. After data are no longer needed, they will be destroyed by the research team, and destruction will be confirmed by the information technology team at the Norris Cotton Cancer Center/Geisel School of Medicine. Further, participants will not be asked to reveal their names or social security numbers. We will ask demographic information, but these self-reported responses will be anonymized and paired with a random Study ID number. Responses will never be linked to any identifying information.

3. **Social media campaign (Phase 3):** The purpose of Phase 3 is to implement and evaluate an educational social media campaign for the public. Based on the results of Phase 1 and 2 studies to-date, we have identified a set of strong messages that improve parent attitudes and increase parents' intent to vaccinate their 9-14 year old child/ren for HPV. We will use these tested messages to launch a social media-based campaign via the Norris Cotton Cancer Center's Facebook page. We will deploy up to six campaign messages (see enclosed document with messages) to two groups of parents using Facebook's geo-targeting features, based on users' zip codes: 1) Parents in rural NH and VT and 2) Parents in urban NH and VT. We will measure each message's effectiveness by analyzing engagement data (provided by social media campaign metrics—all aggregate data with no individual identifiers), and attitudes and intent to vaccinate (to be assessed via online survey embedded in the social media campaign messages). See enclosed survey; parents with children of any age are invited to complete all questions except for questions related to their intention to vaccinate, which are limited to parents with 9-14 year old children. We will compare the differences between the two audience segments (rural vs. urban) and other subgroups that emerge from the data..

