#### 4. Analysis

**Describe any qualitative tests and measures as well as quantitative methods:**

1. **Online and local focus groups and message testing (Phases 1 & 2)-** Facebook comments, survey comments, and transcripts/audio files of the focus groups will be reviewed by the research team and coded for themes. We will also perform content and linguistic analyses. The self-reported survey measures will be examined for outliers and data skewness. Recording, transformation, or standardization will be made when necessary. We will conduct chi-square statistics for categorical variables and employ repeated GLM, ANOVA, ANCOVA, or regression statistics for continuous multivariate variables while controlling for relevant covariates. We will take structural equation modeling or path analyses to model persuasion pathways from message/ad exposure to changes in behavioral intentions to vaccinate. Based on persuasiveness scored rated for the HPV vaccine messages/ads, we will statistically test and select the

most highly-ranked messages/ads (best candidate messages/ads). These selected messages/ads will be used for the social media campaign.

2. **Social media campaign (Phase 3)-** We will measure message effectiveness by analyzing each message's effectiveness by assessing engagement data (provided by social media campaign metrics), and key constructs, including attitudes and intent to vaccinate (to be assessed via online survey embedded in the social media campaign messages). See enclosed survey; parents with children of any age are invited to complete all questions except for questions related to vaccination history and intention to vaccinate their 9-14 year old child/ren, which are limited to parents with 9-14 year old children. We will compare the differences between the two audience segments (rural vs. urban) or other subgroups of interest that emerge from the data. Although we do not solicit comments on Facebook, we expect that some Facebook users may leave comments/questions anyway; we will analyze the comments for themes and linguistic characteristics and compare between rural and urban audiences or by campaign themes (research team will de-identify all comments prior to analyses).

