## 5. Study Progress Monitoring

Note: appropriate monitoring may include periodic assessment of the following:

- data quality
- timelines
- recruitment and enrollment

**Provide a description of the methods which will be used to determine the progress of the study, including periodic assessments of data quality, timelines, recruitment, and enrollment as appropriate:**

The overall project timeline will be reviewed at our research team's weekly meetings, and adjustments will be made as needed to keep on schedule.

1. **Online focus groups/surveys (Phase 1)-** We will monitor the focus group comments under Facebook ads and review the number and themes of the comments in our research team's weekly meetings. Once we achieve either 2,000 comments or sufficient comments to identify strong candidate themes, we will discontinue online focus groups and proceed to message-testing. We will remove comments that are irrelevant or could be unpleasant or emotionally disturbing to others. We will also monitor survey recruitment in our weekly meetings and adjust Facebook ad budget (to increase visibility of the ad among Facebook users) and number of MTurk HIT postings as needed.
2. **Local focus groups/surveys (Phase 2)-** Our team will create a study timeline at the start of any participant recruitment, and we will review the study's progress/timeline at least biweekly. If we are struggling to recruit a sufficient number of participants, we will identify other communication channels to distribute the recruitment messaging.
3. **Online message testing (Phase 2)-** We will monitor the enrollment status on Amazon Mechanical Turk and social media (e.g., Twitter, Facebook), and open more HIT's (Human Intelligence Tasks on MTurk) or Ads (or increase the ad budget). During the data collection period, we will screen the collected data saved in the hosting survey server, and if data are missing at non-random (e.g., missing a whole block of measures), we will follow-up with the subject via Amazon Mechanical Turk, which does not reveal personal information of the individual, to see if s/he wants to drop from the study.

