**Describe potential events and provide a plan of action:**

1. **Online and local focus groups and message testing (Phases 1 & 2)-** It is possible that some messages or comments will have the unintended effects in some audiences (e.g., vaccine-hesitant parents may be even less trusting of the HPV vaccine after viewing other messages or comments). We will debrief parents by providing them with links and/or handouts to learn more about the HPV vaccination (e.g., through the Centers for Disease Control and Prevention or the American Cancer Society) and will suggest that they talk further with their child's physician.
2. **Social media campaign (Phase 3)-** The messages we are using in Phase 3 have already been tested in a national sample of parents and found to improve their attitudes toward HPV vaccination, as well as increase their intention to vaccinate their children (if they have children 9-14 years old). The evaluation survey will include 'debriefing' at the end, including links where they can go to find scientifically-based information about HPV vaccination (e.g., CDC). While we are not soliciting Facebook users to leave any comments or questions on the ad, we expect that some Facebook users will leave comments and questions anyway. If a Facebook user leaves a comment or question, we will respond using the guidelines developed for our team; the idea of generating user interaction guidelines was conceived by [name] as part of the research protocol section, and the guidelines were developed in consultation with the Marketing/Communications teams at Dartmouth-Hitchcock and at the Norris Cotton Cancer Center.

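### Facebook comments may be removed for negative content with no stated saving or coding, while the in-person transcripts they are compared with have no such filter

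*Combined protocol and SAP*

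**What the plan says.** The protocol has two removal rules for Phase 1.

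- **Section 3, item 1 (Focus groups and Survey).** The team says that "we will collect up to 2,000 comments about the themes/questions", and the next sentence reads: "Messages that elicit strong emotional disturbance, negative affect, and negative feedback will be removed from the comments list".
- **Section 5, item 1 (Study Progress Monitoring).** "We will remove comments that are irrelevant or could be unpleasant or emotionally disturbing to others". This stands in the same item as the weekly review of comment numbers and themes and the stopping point, which begins "Once we achieve either 2,000 comments or sufficient comments to identify strong candidate themes".

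Section 4, item 1 (Analysis) then says: "Facebook comments, survey comments, and transcripts/audio files of the focus groups will be reviewed by the research team and coded for themes". It does not mention removed comments.

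The in-person groups serve partly "for determining reliability of the Facebook discussion method" (Section 3, item 1). The local focus group text repeats the aim: "This will enable us to validate the information received during the online focus groups and compare methodologies". The sessions are audio recorded and transcribed. The only stated removal from the transcripts concerns names and identifying information.

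**The concern.** Phase 1 is meant to learn what parents think, including why some hesitate. A rule that removes items according to negative affect or negative feedback acts on the feature the study wants to describe. If it is applied to user comments and the removed ones are not coded, the Facebook list leans towards accepting views.

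The comparison with the in-person groups is the most exposed. It is meant to show whether Facebook discussion yields the same information as a conventional focus group. With a content filter on one side only, a difference between the sources has two possible explanations, and the plan collects nothing that would separate them. If removal also differed between the rural and urban ads, it would blur that contrast as well.

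**Working it through.** **What the text settles and what it leaves open**

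| Question | Section 3, item 1 | Section 5, item 1 | Section 4, item 1 |
|---|---|---|---|
| What is removed | *Messages* provoking disturbance, negative affect and negative feedback | Comments that are irrelevant, or unpleasant or disturbing to others | Not addressed |
| Removed from where | The comments list | Not stated; the context is monitoring of the ads | Not addressed |
| Criteria or rater | None | None | None |
| Before or after theme coding | Not stated | Not stated; it sits beside the theme review and stopping point | Not stated |
| Removed items saved, counted or coded | Not stated | Not stated | Not stated |
| Same rule for in-person transcripts | No | No | No |

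It is also not stated whether the 2,000-comment ceiling counts comments before or after removal. The ceiling is a judgement (Section 9b), so there is no planned calculation to reproduce.

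**Illustration of size**

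The documents give neither a hesitant share nor a removal rate. All inputs here are assumptions:

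- h = true share of Facebook comments that are hesitant
- r = fraction of hesitant comments removed and not coded
- r0 = fraction of other comments removed

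Share of hesitant comments in the coded list = h(1 − r) / [h(1 − r) + (1 − h)(1 − r0)].

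With r0 = 0:

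| h | r | Calculation | Coded share | Fall (percentage points) |
|---|---|---|---|---|
| 10% | 10% | 0.09 / 0.99 | 9.1% | 0.9 |
| 10% | 50% | 0.05 / 0.95 | 5.3% | 4.7 |
| 30% | 10% | 0.27 / 0.97 | 27.8% | 2.2 |
| 30% | 50% | 0.15 / 0.85 | 17.6% | 12.4 |
| 30% | 75% | 0.075 / 0.775 | 9.7% | 20.3 |
| 40% | 50% | 0.20 / 0.80 | 25.0% | 15.0 |
| 40% | 75% | 0.10 / 0.70 | 14.3% | 25.7 |

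Removing some other comments changes little. With h = 30%, r = 50% and r0 = 5%, the share is 0.15 / (0.15 + 0.665) = 18.4%.

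**What this means for the comparison**

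Suppose both methods truly drew 30% hesitant remarks. With half of the hesitant Facebook comments removed, the coded data would show 17.6% online against 30% in person: a gap of 12.4 points with no difference between the methods. The filter can also hide a difference. A true 40% online with half removed becomes 25%, which would match in-person groups that truly ran at 25%.

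**The case against.** The case against has four parts.

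1. **The rules may only be page moderation.** Section 5 speaks of comments disturbing to others, and Section 7 worries that "vaccine-hesitant parents may be even less trusting of the HPV vaccine after viewing other messages or comments". Saving a comment for coding and then hiding it from the page fits that text. Section 4 codes Facebook comments without naming an exclusion. This stands in part: the documents do not state that removal precedes coding. But Section 3 removes items from a list of collected material, on a different criterion from Section 5, and nowhere are removed comments said to be kept.

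2. **The Section 3 sentence may concern candidate messages.** Elsewhere in that section the word usually means the team's own material, and a message elicits feedback whereas a hesitant comment is feedback. On this reading negative comments are used to drop poor messages. The ambiguity is real, although the phrase about a comments list points the other way, and Section 5 does remove comments.

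3. **Hesitant views have other routes in.** This stands. A reader might infer that they are lost from message development, and the documents do not support that. The starting themes come from literature whose examples are hesitant attitudes, the in-person groups help to shape the messages, and no removal rule is stated specifically for the private survey. Theme finding also does not need an accurate share. At 2,000 comments with 20% hesitant and 75% of those removed, 100 of 400 would remain, so the theme could still be found. None of this repairs the comparison, in which the in-person groups are the yardstick.

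4. **The comparison is only a broad aim.** No concordance measure or decision rule is set. So it goes too far to infer that the reliability conclusion cannot be interpreted at all. The supported claim is that a possible bias would go unmeasured.

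**Conclusion.** The point holds in a limited form. The plan has undefined removal rules, one of them tied to negative reactions, with no stated saving, counting or coding of what is removed. Read as rules about comments, they may under-represent hesitant views on the Facebook side only, so disagreement with the in-person groups could reflect the filter and not the method.

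The size cannot be derived from the documents. Under the assumed rates, the fall in the hesitant share runs from about 1 percentage point (10% hesitant, 10% of those removed) to most of the share (30% falling to 9.7%). It is zero if every removed comment is coded anyway, or if the Section 3 rule concerns candidate messages and the Section 5 rule concerns public display alone.

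The text does not establish that all negative comments are removed, or that removal comes before theme identification. It targets items that provoke disturbance or negative reactions, not hesitant comments as such.

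**What to change.** 1. Reword Section 3, item 1 and Section 5, item 1 so that removal applies to public display only. Say whether *messages* means user comments or candidate messages, and define the grounds for hiding a comment.
2. Save every comment before it is hidden.
3. Code the full set, with irrelevant as one of the codes, both for theme finding and for the online versus in-person comparison.
4. Report the number hidden by theme and by rural or urban ad, and give the comparison with and without the hidden comments.

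Section 3, item 3 says that Phase 1 and 2 results to date have already identified strong messages, so Phase 1 collection may be complete. In that case, recode any removed comments that were archived, disclose how many were removed and on what grounds, and qualify the reliability conclusion. Comments that were not archived may not be recoverable, which leaves disclosure.

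The cost is a wording change, a routine export before hiding, and a few more comments to code. Parents viewing the ads keep the same protection, because disturbing comments can still be hidden.
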